2.3 Other Agent(s)

N/A

2.4 Rationale

Previously, our laboratory and others showed that simultaneous targeting of more than one RAS effector pathway (specifically the MEK-ERK (MAPK) and PI3K-AKT pathways) caused marked responses in KRAS-driven mouse tumor models (Engelman et al., 2008; She et al., 2010). While these data support the promise of combination therapy strategies, toxicity has prevented dosing both medications at or near their maximally-tolerated doses when used in combination (LoRusso et al., 2012; Bedard et al., 2012; Speranza et al., 2012). Thus, potent and continuous suppression of the MEK and PI3K pathways may not be possible in patients with currently available agents. Furthermore, this approach may be effective only in a subset or KRAS-mutant cancers. Consequently, additional effective combination therapy strategies for KRAS-mutant cancers are critically needed.

A large-scale screening study of >600 cell lines with >100 targeted compounds identified MEK inhibitors as the most effective agents in KRAS-mutant cell lines (Garnett et al., 2012). However, while MEK inhibition alone leads to decreased proliferation in most KRAS mutant cancers, MEK inhibitors alone typically fail to induce a cell death response ([name] et al., 2013). This observation likely explains why MEK inhibitors have often led to stable disease in KRAS-mutant cancer patients (Infante et al., 2010), but have rarely, if ever, led to true objective tumor responses. Still, because of their potent growth inhibitory effects and their ability to cause disease stabilization in patients with KRAS mutant cancers, MEK inhibitors are a promising backbone for potential combination strategies for KRAS mutant cancers.

Recently, we conducted a pooled shRNA-drug screen to identify promising partners for combination therapy with MEK inhibitors in KRAS mutant cancers ([name] et al., 2013). The top hit from this screen was the anti-apoptotic gene BCL-XL. Pharmacologic inhibition of BCL-XL with the BH3 mimetic navitoclax in combination with a MEK inhibitor led to pronounced apoptosis in the vast majority of 30 KRAS mutant cancer cell lines from different tumor types (pancreas, colorectal, and lung). Apoptosis induction was significantly greater with this inhibitor combination than with either agent alone. Mechanistically, we observed that MEK inhibition alone led to dramatic upregulation of the pro-apoptotic protein BIM. However, immunoprecipitation studies revealed that these increased BIM levels were bound and inhibited by BCL-XL. However, addition of navitoclax blocked the inhibitory interaction of BCL-XL and

BIM, thus "freeing" these elevated levels of BIM protein to promote apoptosis.

In vivo, the combination of navitoclax and a MEK inhibitor led to dramatic tumor regressions in 5 independent KRAS mutant cancer models, and to significantly greater anti-tumor effect than either agent alone. We observed dramatic tumor regressions of established tumors in 3 independent KRAS mutant tumor xenograft models and in 2 genetically-engineered KRAS-driven mouse models of lung cancer (one with mutant p53 and one with wild-type p53). Analysis of treated tumor tissue showed dramatic induction of cell death only in tumors treated with the combination of navitoclax and a MEK inhibitor. These results represent some of the most impressive in vivo preclinical efficacy observed to date with any therapeutic strategy in KRAS mutant cancers.

NRAS activates the same key downstream pathways as KRAS, and NRAS mutant cancers also represent a molecular subtype with few effective treatments. NRAS mutant cancers have shown increased sensitivity to single-agent MEK inhibitors, when compared to KRAS mutant cancers—for example, the MEK inhibitor binimetinib recently exhibited a 15% confirmed response rate in NRAS mutant melanoma patients and extended survival relative to standard chemotherapy. Still, most patients fail to respond and combination therapy strategies are needed.

Thus, we hypothesize that the combination of navitoclax and a MEK inhibitor (trametinib) is a promising novel targeted therapy combination strategy with the potential to lead to tumor responses in patients with KRAS or NRAS mutant cancers of several different tissue types, including melanoma, pancreatic, colorectal, GYN, and lung cancers.

2.5 Correlative Studies Background

2.5.1 Pharmacokinetic Studies

While the pharmacokinetics of trametinib and navitoclax given as single agents is well-understood, this study will evaluate the pharmacokinetics of these agents when given in combination. During the Phase 1b portion of the study, subjects will have blood drawn pre-dose, and 2h, 4h, 6h, 8h, and 23h after dosing on (1) day 7 of a 7-day navitoclax single-agent lead-in dosing period and (2) again after 14 days of combination dosing. Pre-dose (0h) levels of trametinib and navitoclax will also be measured on day 1 of cycles 2, 4, 8 and 12. Plasma concentrations of trametinib will be determined through established procedures by GSK, and concentrations of navitoclax will be determined through established procedures by AbbVie. These studies will be used to determine whether trametinib and navitoclax interact from a pharmacokinetic standpoint, and will be used to determine the maximum observed plasma drug concentration (Cmax), area-under-the concentration-time-curve from zero (pre-dose) to 24 hours (AUC(0-24)), pre-dose (trough) drug concentration for trametinib and navitoclax, and t1/2. Since it is not yet clear whether the single-agent MTDs of these compounds can reached when these agents are dosed in combination, measuring the plasma drug concentrations achieved at

each dose level provide a valuable comparison of the drug exposure achieved at a given dose level to what is known to be achieved at the single-agent MTD.

2.5.2 Pharmacodynamic Studies

This study will incorporate pharmacodynamic analyses to evaluate the effects of trametinib and navitoclax given in combination on key cellular signaling pathways and on the induction of apoptosis and inhibition of tumor cell proliferation. Paired pre-treatment and on treatment core biopsies will be obtained from all patients in the Phase Ib portion of the trial and the first 15 patients enrolled on the Phase 2 portion of the trial (minimum of 4 patients from each of cohorts 1, 2 and 3 will be biopsied), if these patients have lesions that can be safely biopsied without unacceptable risk or discomfort to the patient. Pre-treatment biopsies will be obtained between days -21 and -1 of treatment, and the on-treatment biopsy will be obtained on day 22 (+/-7 days) for patients in the Phase 1b and Part 2 schedule A, and on day 15 (+/-7 days) for patients in the Phase 1b and Part 2 schedule B. Core biopsies of the same tumor lesion will be obtained at each time point. Both fresh frozen and formalin-fixed paraffin-embedded cores will be obtained at each time point.

Paired biopsies will be used to assess the pharmacodynamic response to therapy in these patients. Markers to be assessed will include proteins or mRNAs involved in MAPK or BCL2 family signaling (e.g. phospho-ERK, phospho-S6, or MAPK phosphatases such as DUSP6/MKP1) to evaluate pathway inhibition, markers of tumor cell proliferation (e.g. Ki67), and markers of apoptosis and cell death (e.g. Cleaved caspase-3). For each patient, the change in marker level between the pre-treatment and on-treatment (day 15) biopsies will indicate the effects of treatment on each marker. Other potentially important biomarkers identified in emerging laboratory investigations may also be evaluated.

Biopsies from patients in the Phase Ib portion of the trial will provide an evaluation of the effects of each cohort's dose level on signaling pathway inhibition, inhibition of tumor cell proliferation, and induction of tumor cell death. This will provide an important metric as to the extent of target inhibition at each given dose level. Paired biopsies obtained from the first 15 patients enrolled in the Phase 2 portion of the trial (minimum of 4 patients from each of cohorts 1, 2 and 3 will be biopsied) will provide a more detailed assessment of the pharmacodynamic effects of therapy at the RP2D and will offer the potential to correlate pharmacodynamic effects with tumor response and patient outcome.

2.5.3 Predictive Biomarker Analysis in Pre-Treatment Biopsies

Given the molecular heterogeneity of KRAS and NRAS mutant cancers, no single therapeutic regimen is expected to be effective in all patients. Therefore, molecular characterization of archived or pre-treatment tumor biopsy tissue for each patient enrolled on this trial will provide a critical opportunity to identify valuable biomarkers to predict which patients are more or less likely to respond to treatment.

2.5.3.1 Mutational Analysis

Extensive tumor mutational analysis of 1000 genes will be performed for each patient using a next-generation genotyping platform employed as part of standard oncology care at the Massachusetts General Hospital Cancer Center. Mutations in key pathways that might affect the likelihood of a patient's tumor to respond to therapy (e.g. PIK3CA, PTEN, p53, etc.) will be correlated with objective tumor response or PFS. Additional in-depth genomic analyses, including copy number analyses, may also be performed.

2.5.3.2 Biomarker Expression Analysis

We also plan analysis of selected protein and mRNA biomarkers identified in previous (and future) laboratory studies. For example, our initial laboratory studies ([name] et al., Cancer Cell, 2013) have suggested that KRAS mutant cancers that express markers of epithelial differentiation (e.g. E-cadherin) are more likely to respond to this therapy that cancers expressing markers of mesenchymal differentiation (e.g. vimentin). Thus, E-cadherin and vimentin levels will be assessed by immunohistochemistry in archived or pre-treatment biopsies. Also, baseline levels of specific BCL2 family apoptotic proteins, including BCL-XL, MCL1, and BIM, have also been shown to predict responsiveness to this therapy in laboratory models. These markers will also be assessed. Biomarker levels will be correlated with response rate or PFS and may help identify which subpopulation of KRAS or NRAS mutant cancer patients are more or less likely to response therapy.

3. PATIENT SELECTION

3.1 Eligibility Criteria

- 3.1.1 Patients must have histologically- or cytologically-confirmed diagnosis of KRAS or NRAS mutation-positive malignancy that is metastatic or unresectable and for which standard curative measures do not exist or are no longer effective. Patients must have activating mutations affecting codons 12, 13, 61, or 146 as determined in a CLIA certified lab to be eligible for this study.
- 3.1.2 Patients must have measurable disease by RECIST, defined as at least one lesion that can be accurately measured in at least one dimension (longest diameter to be recorded for non-nodal lesions and short axis for nodal lesions) as ≥20 mm by chest x-ray or as ≥10 mm with CT scan, MRI, or calipers by clinical exam. See Section 11 for the evaluation of measurable disease.

Version Date: July 22, 2022

3.1.3 Participants must have received at least one line of prior systemic chemotherapy and must have experienced documented radiographic progression or intolerance on this therapy.

- 3.1.4 Paired pre-treatment and post-treatment biopsies are required for all patients on Part 1 and first 15 patients in Part 2. Participants must have available archival tumor tissue (at least 20 unstained slides.) If archival tissue is not available or is found not to contain tumor tissue, a fresh biopsy is required. If a patient is having a tumor biopsy, less than 20 unstained slides are acceptable with approval of the PI. Biopsies will only be performed in a given patient if they are not deemed to involve unacceptable risk based on the sites of disease and other concurrent medical conditions.
- 3.1.5 Age \geq 18 years.

Because no dosing or adverse event data are currently available on the use of trametinib in combination with navitoclax in patients <18 years of age, children are excluded from this study, but will be eligible for future pediatric trials.

- 3.1.6 ECOG performance status ≤ 1 (see Appendix A).
- 3.1.7 Life expectancy of greater than 3 months
- 3.1.8 Able to swallow and retain orally-administered medication and does not have any clinically significant gastrointestinal abnormalities that may alter absorption such as malabsorption syndrome or major resection of the stomach or bowels.
- 3.1.9 All prior treatment-related toxicities must be CTCAE v4 grade ≤1 (except alopecia) at the time of enrollment. This requirement to return to ≤ grade 1 does not apply to immune checkpoint inhibitor related endocrinopathies (e.g. thyroiditis, hypophysitis, etc.) that necessitate hormone replacement therapy including, but not limited to levothyroxine, cortisol, and testosterone. CTCAE v5.0 will be utilized beginning April 1, 2018.
- 3.1.10 Patients must have normal organ and marrow function as defined below:
 - Leukocytes $\geq 3,000$ /mcL
 - Absolute neutrophil count (ANC) ≥1,200/mcL (subjects may be treated with hematopoietic growth factors to achieve or maintain this level)
 - Hemoglobin ≥9 g/dL
 - Platelets $\geq 100 \times 10^9 / L$
 - Albumin >2.5 g/dL
 - Total bilirubin ≤1.5x institutional ULN (patients with Gilbert's syndrome may have serum bilirubin >1.5×ULN)
 - Aspartate aminotransferase (AST) and alanine aminotransferase (ALT) ≤2.5x institutional ULN

- Serum creatinine ≤1.5 mg/dL *OR* calculated creatinine clearance (Cockroft-Gault formula) ≥50 mL/min *OR* 24-hour urine creatinine clearance ≥50 mL/min
- Prothrombin time (PT)/International normalized ratio (INR) and partial thromboplastin time (PTT) \leq 1.2x institutional ULN
- Left ventricular ejection fraction ≥ institutional lower limit of normal (LLN) by ECHO or MUGA
- 3.1.11 The effects of trametinib and navitoclax on the developing human fetus are unknown. For this reason, women of child-bearing potential and men with a female partner of child bearing potential must agree to use adequate contraception using *one of the methods listed below* prior to study entry, for the duration of study participation, and up to 4 months following completion of therapy.
 - total abstinence from sexual intercourse (minimum one complete menstrual cycle prior to study drug administration);
 - Vasectomized male subject or vasectomized partner of female subjects;
 - Hormonal contraceptives (oral, parenteral, transdermal or vaginal ring) for at least 3 months prior to study drug administration; if the subject is currently using a hormonal contraceptive, she should also use a barrier method during this study and for 1 month after study completion;
 - intrauterine device (IUD);
 - double-barrier method: male condom plus diaphragm or vaginal cap with spermicide (contraceptive sponge, jellies or creams);

Men with a female partner of childbearing potential must have either had a prior vasectomy or agree to use effective contraception. Additionally, male subjects (including those who are vasectomized) whose partners are pregnant or might be pregnant must agree to use condoms for the duration of the study and for 4 months following completion of therapy.

Women of childbearing potential must have a negative serum pregnancy test within 7 days prior to initiation of treatment. Women will be considered not of childbearing potential if they are surgically sterile (bilateral oophorectomy or hysterectomy) and/or post-menopausal (amenorrheic for at least 12 months).

Should a woman become pregnant or suspect she is pregnant while she or her partner is participating in this study, she should inform her treating physician immediately. The potential hazard to the fetus should be explained to the patient and partner (as applicable).

3.1.12 Ability to understand and the willingness to sign a written informed consent document.

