11.1.1 Definitions

Evaluable for toxicity. All patients will be evaluable for toxicity from the time of their first treatment with navitoclax and/or trametinib.

Evaluable for objective response. Only those patients who have measurable disease present at baseline, have received at least one cycle of therapy, and have had their disease re-evaluated will be considered evaluable for response. These patients will have their response classified according to the definitions stated below. (Note: Patients who exhibit objective disease progression prior to the end of cycle 1 will also be considered evaluable.)

Evaluable Non-Target Disease Response. Patients who have lesions present at baseline that are evaluable but do not meet the definitions of measurable disease, have received at least one cycle of therapy, and have had their disease re-evaluated will be considered evaluable for non-target disease. The response assessment is based on the presence, absence, or unequivocal progression of the lesions.

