11.1.2 Disease Parameters

Measurable disease. Measurable lesions are defined as those that can be accurately measured in at least one dimension (longest diameter to be recorded) as \geq 20 mm by chest x-ray or as \geq 10 mm with CT scan, MRI, or calipers by clinical exam. All tumor

p: Off study procedures should be performed within 14 days of last dose. Patients will be followed until the resolution or stabilization of all study-related toxicity and for a minimum of 30 days after removal from study or until death, whichever occurs first. Patients removed from study for unacceptable adverse event(s) will be followed until resolution or stabilization of the adverse event.

measurements must be recorded in millimeters (or decimal fractions of centimeters).

Note: Tumor lesions that are situated in a previously irradiated area might or might not be considered measurable. *If the investigator thinks it appropriate to include them, the conditions under which such lesions should be considered must be defined in the protocol.*

Malignant lymph nodes. To be considered pathologically enlarged and measurable, a lymph node must be ≥ 15 mm in short axis when assessed by CT scan (CT scan slice thickness recommended to be no greater than 5 mm). At baseline and in follow-up, only the short axis will be measured and followed.

Non-measurable disease. All other lesions (or sites of disease), including small lesions (longest diameter <10 mm or pathological lymph nodes with ≥10 to <15 mm short axis), are considered non-measurable disease. Bone lesions, leptomeningeal disease, ascites, pleural/pericardial effusions, lymphangitis cutis/pulmonitis, inflammatory breast disease, and abdominal masses (not followed by CT or MRI), are considered as non-measurable.

Note: Cystic lesions that meet the criteria for radiographically defined simple cysts should not be considered as malignant lesions (neither measurable nor non-measurable) since they are, by definition, simple cysts.

'Cystic lesions' thought to represent cystic metastases can be considered as measurable lesions, if they meet the definition of measurability described above. However, if non-cystic lesions are present in the same patient, these are preferred for selection as target lesions.

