13.5.2 Evaluation of Response

All patients included in the study must be assessed for response to treatment, even if there are major protocol treatment deviations or if they are ineligible. Each patient will be assigned one of the following categories: 1) complete response, 2) partial response, 3) stable disease, 4) progressive disease, 5) early death from malignant disease, 6) early death from toxicity, 7) early death because of other cause, or 9) unknown (not assessable, insufficient data). [Note: By arbitrary convention, category 9 usually designates the "unknown" status of any type of data in a clinical database.]

All of the patients who met the eligibility criteria (with the possible exception of those who received no study medication) should be included in the main analysis of the response rate. Patients in response categories 4-9 should be considered to have a treatment failure (disease progression). Thus, an incorrect treatment schedule or drug administration does not result in exclusion from the analysis of the response rate. Precise definitions for categories 4-9 will be protocol specific.

All conclusions should be based on all eligible patients. Sub analyses may then be performed on the basis of a subset of patients, excluding those for whom major protocol deviations have been identified (*e.g.*, early death due to other reasons, early discontinuation of treatment, major protocol violations, etc.). However, these sub analyses may not serve as the basis for drawing conclusions concerning treatment efficacy, and the reasons for excluding patients from the analysis should be clearly reported. The 95% confidence intervals should also be provided.

REFERENCES

Balagula, Y., K. Barth Huston, K.J. Busam, *et al.* (2010). Dermatologic side effects associated with the MEK 1/2 inhibitor selumetinib (AZD6244, ARRY-142886). *Invest New Drugs*. 29:1114-1121.

Bekaii-Saab, T., M.A. Phelps, X. Li, *et al.* (2011). Multi-institutional phase II study of selumetinib in patients with metastatic biliary cancers. *J Clin Oncol.* 29:2357-2363.

Bendell, J., P. LoRusso, E. Kwak, *et al.* (2011). Clinical combination of the MEK inhibitor GDC-0973 and the PI3K inhibitor GDC-0941: A first-in-human phase Ib study in patients with advanced solid tumors. *AACR Meeting Abstracts*. Abstract LB-89.

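### Section 3.1.2 accepts a 10 mm node as measurable disease and Section 11.1.2 requires 15 mm, so patients for whom a partial response is undefined can enter the response analysis and bias it in either direction

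*Combined protocol and SAP*

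**What the plan says.** **Entry.** Section 3.1.2 requires at least one accurately measurable lesion. Lesions outside nodes are taken by longest diameter, and the rest of the definition runs: "short axis for nodal lesions) as ≥20 mm by chest x-ray or as ≥10 mm with CT scan, MRI, or calipers by clinical exam". It gives no separate size for nodes, and it closes with a pointer: "See Section 11 for the evaluation of measurable disease".

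**Measurement.** Section 11.1.2 uses the same 20 mm and 10 mm limits for lesions in general, then adds a node rule that 3.1.2 lacks: a "lymph node must be ≥ 15 mm in short axis when assessed by CT scan". It goes on to state that "pathological lymph nodes with ≥10 to <15 mm short axis), are considered non-measurable disease".

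**Response.** Target lesions are drawn from measurable lesions (11.1.2). PR is a shrinkage of at least 30% in the sum of target-lesion diameters (11.1.4.1). The table for non-measurable disease in 11.1.4.3 has a CR row and no PR row. Non-target CR requires all non-target lesions to disappear, nodes to be under 10 mm in short axis, and raised tumor markers to normalize (11.1.4.2). The Part 2 response endpoint is PR plus CR (13.1.2.2).

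**Denominator.** Section 11.1.1 restricts evaluability for objective response: "Only those patients who have measurable disease present at baseline, have received at least one cycle of therapy" and have been re-evaluated. Section 13.5.2 says that patients who met the eligibility criteria "should be included in the main analysis of the response rate", and adds: "All conclusions should be based on all eligible patients".

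**The concern.** Section 3.1.2 names the short axis of nodes in the same sentence as the 10 mm limit, so that limit cannot be read as covering non-nodal lesions only. A site that applies 3.1.2 as written can enrol a patient whose sole qualifying lesion is, say, a 12 mm node. Under Section 11 that patient has no target lesion, so the PR part of the primary endpoint is undefined. The only route to response is CR under different rules from those applied to the rest of the cohort.

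Two things are at stake. The first is whether the response rate in a cohort means the same thing for every patient in it. The second is the denominator: the two sections that define it give opposite answers for this patient. The decision rules turn on very few responses (none among 12 closes a cohort; three among 25 make the regimen promising), so one or two such patients can matter.

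**Working it through.** **Inputs from Section 13.1.2.** Stage 1 has 12 patients and stops on 0 responses. Stage 2 adds 13. The regimen is promising with at least 3 responses among 25. Null rate 5%, target rate 17%. Stated error rates: 11% false-positive, 22% false-negative, 54% early stopping at 5%.

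**Formula.** With X1 ~ Bin(12, p) and X2 ~ Bin(13, p):

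P(promising) = 1 − P(X1=0) − P(X1=1)·P(X2≤1) − P(X1=2)·P(X2=0)

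**Reproducing the plan.**
- p = 0.17: 1 − 0.1069 − 0.2627 × 0.3249 − 0.2960 × 0.0887 = 0.781, so the false-negative rate is 21.9%.
- p = 0.05: 1 − 0.5404 − 0.3413 × 0.8646 − 0.0988 × 0.5133 = 0.114. Early stopping is 0.95^12 = 0.540.

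All three match the stated figures.

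**Case 1: affected patients never respond.** Removing k patients from those able to respond lowers the binomial sizes and leaves the decision rules unchanged. The number affected is an assumption.

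| Able to respond (stage 1 + stage 2) | Power at 17% |
|---|---|
| 12 + 13 | 78.1% |
| 11 + 13 (one affected, stage 1) | 75.1% |
| 12 + 12 (one affected, stage 2) | 76.4% |
| 11 + 12 (one affected in each stage) | 73.2% |

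With one affected patient in stage 1, the chance of closing a cohort whose true rate is 17% rises from 0.83^12 = 10.7% to 0.83^11 = 12.9%.

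**Case 2: affected patients can reach CR.** Let f be the share affected and q their CR probability, taken as the same whether or not the drug works. The cohort rate is then p(1 − f) + qf. Neither f nor q is in the documents. At f = 10%:

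| q | Rate if p = 17% | Power | Rate if p = 5% | False-positive |
|---|---|---|---|---|
| 0 | 15.3% | 71.5% | 4.5% | 9.0% |
| 5% | 15.8% | 73.6% | 5.0% | 11.4% |
| 17% | 17.0% | 78.1% | 6.2% | 18.0% |
| 25% | 17.8% | 80.8% | 7.0% | 22.9% |

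**Which direction is plausible?** A lone 12 mm node falls under the nodal CR size with a little over (12 − 10)/12 = 17% shrinkage, against 30% for a PR. Any node below 10/0.7 = 14.3 mm that shrinks by 30% also passes under 10 mm. For isolated small nodes, then, response may be easier to reach than for other patients. Where the node coexists with bone lesions, ascites or effusion (all non-measurable under 11.1.2), or with raised markers, CR requires all of that to clear or normalize, and response is harder.

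**The case against.** The strongest answer is that 3.1.2 asks for measurable disease by RECIST and refers the reader to Section 11, which adopts RECIST 1.1 and states the 15 mm node rule outright. A site that follows the pointer would not count a 12 mm node, and the number enrolled this way might be zero. That stands as a limit on how often the problem arises. It does not cure the wording, because 3.1.2 supplies a definition of its own that differs from the section it points to.

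A second answer is that 11.1.1 already keeps such patients out of the response-evaluable set. That is one of two readings. Section 13.5.2 bases the main analysis and all conclusions on eligible patients, and the plan does not say which section governs.

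A reader might also infer that these patients cannot respond at all, so that they necessarily lower the response rate and power and take up stage 1 places that could never open stage 2. The documents do not support that. The endpoint includes CR, the table for non-measurable disease allows it, and the nodal size it requires is within reach of modest shrinkage. Only PR is closed to them.

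**Conclusion.** The contradiction between 3.1.2 and 11.1.2 is real, and so is the conflict between 11.1.1 and 13.5.2 over whether the affected patients count. The direction of the bias is not settled. It is downward if other non-measurable disease or raised markers must also clear for CR, and upward if slight shrinkage of a small node is scored as CR.

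The power losses in Case 1 (about 2 to 5 points with one or two such patients) are worst-case figures that assume no responses among them. The rise in false positives to about 23% rests on an assumed 10% share and an assumed 25% CR rate unrelated to drug effect. With no affected patients, the stated operating characteristics hold exactly. The case for correction is that the entry and response rules disagree and the remedy is cheap; it does not depend on a demonstrated loss of power.

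**What to change.** 1. Amend 3.1.2 to carry the Section 11 thresholds: at least 10 mm longest diameter for non-nodal lesions by CT, MRI or calipers, and at least 15 mm short axis for nodes by CT.
2. Reconcile 11.1.1 with 13.5.2: state one denominator for the primary response rate and for the 12- and 25-patient decision rules, and say how a patient without measurable disease at baseline is handled.
3. For patients already enrolled, identify any who qualified only on a node of 10 to under 15 mm, and report the cohort response rate with and without them.

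The first change is one line and makes a few patients with only small nodes ineligible. The second is a short text edit. The third needs a check of baseline lesion records. None of them alters treatment or the sample size.
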